2.1.1.2 Generalizability of results

Brain and other nervous system cancer is most frequently diagnosed among people ages 55-64 according to the National Cancer Institute's Surveillance, Epidemiology, and End Results Program (SEER). The percent of brain and other nervous system cancer deaths is highest among people aged 65-74, with the median age 58 at diagnosis and 65 at death. Given the impact of brain and nervous system cancer on the general older patient population, results from this investigation will be additive to the cancer knowledge landscape for scientists and investigators going forward.

2.1.2 Background

2.1.2.1 Introduction to Electric Fields

In the laboratory setting and in clinical practice, alternating electric fields show a wide range of effects on living tissues. At very low frequencies (under 1 kHz), alternating electric fields stimulate excitable tissues through membrane depolarization [29]. The transmission of such fields by radiation is insignificant and therefore they are usually applied directly by contact electrodes, though some applications have also used insulated electrodes. Some well-known examples of such effects include nerve, muscle and heart stimulation by alternating electric fields [29, 30]. In addition, low frequency pulsed electric fields have been claimed to stimulate bone growth and accelerate fracture healing [31]. However, as the frequency of the alternating electric field increases above 1 kHz, the stimulatory effect diminishes. Under these conditions although a greater fraction of the fields penetrates the cells, due to the parallel resistor-capacitor nature of all biological membranes, the stimulatory power greatly diminishes as the alternating cell membrane hyper-depolarization cycles are integrated such that the net effect is nulled.

At very high frequencies (e.g. MHz), while the integration becomes even more effective, a completely different biological effect is observed. At these frequencies tissue heating becomes dominant due to dielectric losses. This effect becomes more intense as field intensity or tissue dissipation factor increase [32]. This phenomenon serves as the basis for some commonly used medical treatment modalities including diathermy and radio frequency tumor ablation, which can be applied through insulated electrodes [33].

Intermediate frequency electric fields (i.e., tens of kHz to MHz), alternate too fast for causing nerve-muscle stimulation and involve only minute dielectric losses (heating). Such fields, of low to moderate intensities, are commonly considered to have no biological effect [32]. However, a number of non-thermal effects, of minor biological consequence, have been reported even at low field intensities. These include microscopic particle alignment (i.e., the pearl chain effect [34]) and cell rotation [35, 36]. With pulsed relatively strong electric fields, >

103 V/cm and 100 ms pulse length, reversible pore formation appears in the cell membrane, a phenomenon usually called electroporation [37].

2.1.2.2 Novocure's Tumor Treating Electric Fields (TTFields)

Novocure has shown [38] that when properly tuned, very low intensity, intermediate frequency electric fields (TTFields) stunt the growth of tumor cells. This inhibitory effect was demonstrated in all proliferating cell types tested, whereas, non-proliferating cells and tissues were unaffected. Interestingly, different cell types showed specific intensity and frequency dependences of TTField inhibition. It has been shown that two main processes occur at the cellular level during exposure to TTFields: arrest of proliferation and dividing cell destruction. The damage caused by TTFields to these replicating cells was dependent on the orientation of the division process in relation to the field vectors, indicating that this effect is non-thermal. Indeed, temperature measurements made within culture dishes during treatment and on the skin above treated tumors in-vivo, showed no significant elevation in temperature compared to control cultures/mice. Also, TTFields caused the dividing cells to orient in the direction of the applied field in a manner similar to that described in cultured human corneal epithelial cells exposed to constant electric fields [39]. At the sub-cellular level, it was found that TTFields disrupt the normal polymerization-depolymerization process of microtubules during mitosis. Indeed, the described abnormal mitotic configurations seen after exposure to TTFields are similar to the morphological abnormalities seen in cells treated with agents that interfere directly [40, 41] or indirectly [42-44] with microtubule polymerization (e.g. paclitaxel).

2.1.2.3 The Optune Device

The Optune system (NovoTTF™ Therapy) is a portable battery- operated device, which produces TTFields within the human body by means of surface transducer arrays [45-47]. The TTFields are applied to the patient by means of surface transducer arrays that are electrically insulated, so that resistively coupled electric currents are not delivered to the patient. The transducer arrays, which incorporate a layer of adhesive hydrogel and a layer of hypoallergenic medical tape, are placed on the patient's shaved head. The transducer arrays must be replaced every three to four days and the scalp re-shaved in order to maintain optimal capacitative coupling between the transducer arrays and the patient head. All the treatment parameters are pre-set by Novocure so there are no electrical output adjustments available to the patient. Patients and their caregivers are instructed on proper procedures for changing and recharging depleted service batteries and connecting the device to an external battery pack overnight.

Optune is currently FDA-approved as a single modality treatment for recurrent GBM when both surgical and radiotherapy options have been exhausted. In the pivotal EF-11 trial in recurrent GBM, overall survival (OS) of patients treated with the device was equivalent to those treated with standard chemotherapy alone [46]. Six-month progression-free survival (6PFS) analysis favored the TTFields arm compared to the chemotherapy arm, although not statistically significant. Safety and toxicity profile favored the Optune arm compared to the chemotherapy control arm. No device-specific grade 3 and 4 toxicities were identified for hematologic, gastrointestinal, vascular, renal and respiratory disorders. There were also no increased grade 3 and 4 central nervous system adverse events. The most common device specific adverse event was skin rash due to the transducer arrays. In 2017, Optune was approved in combination with first-line adjuvant temozolomide for newly diagnosed GBM (see below).

2.1.2.4 Effect of Optune on Newly Diagnosed GBM Patients - A Phase 3 Study

Six-hundred ninety-five patients from 83 centers across the world were treated. All patients underwent surgery and radiotherapy for the primary tumor. All patients received temozolomide as adjuvant chemotherapy and were then randomized to standard adjuvant temozolomide chemotherapy (for 6-12 cycles) with or without concomitant administration of TTFields. There was a 2.7- month PFS increase with a median PFS of 6.7 months compared to 4.0 months in the control group (HR, 0.63; 95% CI, 0.52-0.76; $P < .001$) [47, 48]. Median overall survival results increased from 16 months in the temozolomide alone group to 20.9 months in the TTFields plus adjuvant temozolomide group

(HR, 0.63; 95% CI, 0.53-0.76; $P < .001$). [48] Systemic adverse event frequency was 48% vs. 44% in the combination arm vs. temozolomide alone arm, respectively. These results established a new standard treatment for newly diagnosed GBM [47, 48].

2.1.2.5 Temozolomide

Adjuvant temozolomide and radiation therapy following surgery has been shown to improve survival by about 20%. According to the temozolomide package insert adjuvant temozolomide treatment delays disease progression (from 5 to 6.9 months) and improves overall survival (from 12.1 to 14.6 months) in classical GBM histology [25].

2.1.2.6 Correlative Study Background

2.1.2.6.1 THE IMMUNOLOGICAL BASIS BEHIND TTFIELDS

Although immunotherapy, especially immune checkpoint inhibitors (ICIs), has proven to be efficacious against many cancers including lung, head and neck, renal and urothelial cancers, melanoma and lymphoma, their activities against poorly immunogenic cancers such as malignant gliomas remain less defined. Several intratumoral factors have been identified to correlate with responses to ICIs. 1) Mutational burden and landscape have been demonstrated to predict response to ICIs in several cancers, through various mechanisms including correlation between high mutational burden and higher checkpoint ligand expression [49-51], and the observation that effective anti-tumor immune response can be elicited against tumor neoantigens, which are more abundant in tumors with higher mutational burden [52, 53]. Tumors with high mutational burden due to microsatellite instability and/or defective mismatch repair mechanisms have some of the highest response rates to ICIs [54-61]. 2) The presence of tumor infiltrating lymphocytes (TILs), particularly CD8+ TILs, has also been correlated with response to ICIs [62]. TILs may help drive expression of PD-L1 expression in tumors [63]. However, the composition of TILs is emerging as a more reliable predictor of outcomes and response to ICIs. TILs composed mostly of type 1 T cells with high TBET expression and type 1 interferon response are associated with better outcomes, whereas TILs enriched in regulatory T cells expressing the forkhead box transcription factor (Foxp3) (Tregs) confer a significantly poor prognosis and severe resistance to ICIs [64].

Gliomas are generally considered to have low mutation burden compared to ICI-sensitive tumors [65]. The combination of radiotherapy and temozolomide, an alkylating agent, has been suggested to increase mutation burden in gliomas [66], however it remains unclear if this modest increase was sufficient to improve response to ICIs. Early clinical experience of ICIs in recurrent malignant gliomas showed minimal efficacy [67, 68]. However high-grade gliomas with a hypermutant phenotype, such as in patients with germline biallelic mismatch repair deficiency, demonstrated significant and durable response to ICIs [69], indicating that very high mutation burden may improve gliomas' response to ICIs. Recent study in an animal model of lung cancer suggested that TTFIELDS targeted DNA repair mechanisms [70], which potentially could greatly enhance mutation burden in treated tumors over time. These results raise the possibility that the addition of TTFIELDS to chemoradiotherapy in glioma treatment may be sufficient at increasing mutation burden above the threshold of necessary for meaningful and durable response to ICIs. Although immunotherapy and ICIs are not the focus of the current protocol, we propose to determine whether TTFIELDS can indeed increase mutation burden since the results will have significant impact for future trials and treatment development for gliomas in general. Tumor mutational burden will be assessed by standard clinical DNA sequencing on pre-treatment (i.e. at initial surgery) and post-treatment (i.e. first radiographic recurrence while receiving adjuvant temozolomide and TTFIELDS and any subsequent recurrences, where available from standard care procedures) tumor specimens. These results will be compared to historical and concurrent data available on patients with malignant gliomas similarly treated at participating institutions with radiation and temozolomide only and without TTFIELDS. Both microsatellite status and mutation burden, expressed as number of mutations per Mb, will be obtained and compared between the 2 groups.

Radiographic responses to TTFIELDS have been noted to be delayed, in many instances, for >4 months after treatment initiation. In fact, most responders to TTFIELDS experienced transient increases in enhancement, FLAIR and vasogenic edema within 2-4 months of treatment initiation, followed by a gradual decrease in enhancement and edema (EF-11 and EF14 study) [46, 47]. These observations suggest a possibility that TTFIELDS may induce an inflammatory reaction in the tumor. In animal models of cancer, TTFIELDS therapy to the primary tumors induced a considerable increase in peri- and intra-tumoral immune cell infiltration, including both CD4⁺ and CD8⁺ lymphocytes, compared to sham-treated control tumors [71]. Although the mechanism remains unclear, it is presumably through its anti-mitotic activities causing immunogenic cell death of cancer cells, leading to an increase in cancer-associated antigen or neoantigen presentation and immune activation, including type 1 interferon responses. In this protocol, we will seek to confirm these observations using patients' tissue samples with an eye toward future combinations of TTFIELDS and immunotherapy.

2.1.2.6.2 THE PHYSICS THAT GOVERNS TTFIELDS

TTFIELDS are lower frequency electromagnetic energies operating at 200 kHz and they are administered externally on the scalp by the Optune® device that consists of two pairs of transducer arrays positioned orthogonally from each other and are connected to a portable electric field generator [72]. The distribution of these electric fields within the intracranial space is governed by the laws of physics, specifically Coulomb's Law, Gauss' Law, Ohm's Law and the principles of continuity and capacitance. Derivatives of these laws also comprise principles such as capacitive reactance and specific absorption rate, which are critical for the characterization of the respective electric field distribution and power absorption rate within the brain [73]. Furthermore, the distribution of TTFIELDS are dependent on tissue characteristics, such as physical density, geometry, electric conductivity and relative permittivity, which in turn determine the changing magnitude and direction of the flow of electric charges flow through different regions of the brain as a function of time. Preclinical experiments have shown that TTFIELDS at 200 kHz interfere with dividing cancer cells as they undergo the metaphase-to-anaphase transition in mitosis with evidence that they may perturb the functions of α/β Tubulin and Septin 2,6,7 protein complex, both of which possess high dipole moments, leading to cellular stress, transcriptional alteration and dysfunctional DNA repair [38, 70, 74]. However, the modeling of TTFIELDS in the brain and therefore treatment verification requires complex computational simulation and modeling of electromagnetic wave propagation, which entails added difficulties due to the different conductivity and relative permittivity values of various intracranial tissues and cavities [73, 75, 76].

In order to visualize the distribution of TTFIELDS in the tumor and the surrounding brain tissues, the coupled Maxwell equations must be solved using numerical approximations such as finite element modeling. These computer modeling procedures involve the segmentation of various brain tissues as seen on patient MRI datasets, the application of appropriate initial and boundary conditions and material properties and finding the solution to the coupled Maxwell equations using finite element analysis. A heatmap of the electric field distribution within the human brain can be derived as well as the electric field-volume and specific absorption ratio-volume histograms can be constructed [73]. From these histograms, the electric field parameters, including E_{AUC} , E_{V150} , $E_{95\%}$ and $E_{50\%}$, as well as specific absorption ratio parameters, including SAR_{AUC} , $V_{SAR7.5}$, $SAR_{95\%}$ and $SAR_{50\%}$, can then be used to compare the dosage applied to different patients. Past effort has shown that the electric field strength estimated by computer modeling was within 10% of that measured directly [45]. However, aggregate analysis is lacking on a larger homogeneous patient population that has been treated by TTFIELDS. Therefore, in this protocol, we will perform computer modeling of electric field and energy deposition in the tumor and then perform correlative analysis with respect to overall survival, progression-free survival and response.

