6.3.2 Electric Field Modeling

Tumor Treating Fields are alternating electric fields at 200 kHz that can penetrate from the surface of the scalp into the brain to exert their anti-mitosis effect on dividing tumor cells. They have to first pass through the calvarium and subarachnoid space where they are attenuated by resistive property of bone and the conductive property of the cerebrospinal fluid. The remaining fields then reach the gray and white matters where they are either augmented or attenuated, depending on the local tissue properties and the geometry of structures such as the frontal, temporal and posterior horns of the lateral ventricles. As a result of these interferences, the amount of electric fields that reaches the gross tumor volume cannot be calculated precisely but can only be approximated numerically by methods such as finite element analysis [62].

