6.3.2.1 Secondary imaging analyses

In addition, secondary analyses will be performed to determine the extent of correlation with respect to patient age, Karnofsky Performance Status, dexamethasone dosage, other non-therapeutic supportive medications and the number of cycles of chemotherapy, targeted therapy, biological agents or immune therapies received.

Additional analyses will be conducted to also determine the correlation with fluctuations in laboratory values in complete blood counts, differential, electrolytes, liver function tests, as well as histological and genetic

parameters, such as Ki67, presence or absence of IDH-1 mutation, MGMT methylation status and/or somatic mutations found in next generation sequencing.

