6.3.2.2 MRI Acquisition and DICOM images

The process of numerical estimation of electric field strength at the gross tumor volume consists of a number of steps. First, gadolinium-enhanced MP RAGE sequences will be acquired using MRI in one axis and reconstructed in the other two axes resulting in axial, coronal and sagittal images. Standard T2, FLAIR and pre-gadolinium sequences will also be obtained per local care standards. The field of view of the images should include the surface of the scalp (Fig. 7). These images will be exported as DICOM images.

Second, the DICOM images will be imported into a tissue segmentation software program as previously described [69]. Third, both intracranial and extracranial structures, including scalp, skull, dura, cerebrospinal fluid, gray matter, white matter and bilateral ventricles, will be segmented and meshed before solving using finite element methods [62].

Lastly, the electric field strength and the specific absorption ratio at the gross tumor volume will be tabulated using various electric field strength parameters, including EAUC, EV150, E95% and E50%, and specific absorption ratio parameters, including SARAUC, VSAR7.5, SAR95% and SAR50%. Together, these parameters will allow the comparison among patients of the electric field strength, as well as the amount of energy deposited, at the tumor.

The electric field and specific absorption ratio parameters will be correlated with measures of clinical outcome, including response rate, progression free survival and overall survival. Spearman rank-order correlation will be performed between the non-parametric electrical and clinical outcome variables.

The DICOM images will be obtained for analysis at baseline, each two months per protocol, and at the time of first and second progression. These analyses will be performed at Beth Israel Deaconess Medical Center. Analysis will be completed within two years of the last patient's enrollment.

[figure not shown]

Figure 7. MRI image samples demonstrating field of view of the images must include the surface of the scalp. Incorrect image on the left does not include full scalp surface where indicated by arrows. The correct image at the right does include the surface of the scalp around the entire head.

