10.2.1 Analysis of Primary and Secondary Endpoints and Correlative Studies

We will compare OS and progression-free survival (PFS) between historical control and experimental treatment arms using the log-rank test (we will also collect PFS data via chart review for the historical control patients). For our correlative studies, we will use the independent-sample t test to compare mean mutation burden between patient samples treated with RT+temozolomide or RT+temozolomide+TTFields. We may perform the same comparison within a linear regression framework if the need arises to adjust for any potential confounders for the effect of TTFields in our correlative studies.

To investigate the influence of electric field and energy deposition in the tumor on outcomes, we will use the Wilcoxon rank sum test to compare the electric field and specific absorption ratio parameters between: responders and non-responders; subjects with progression-free survival \geq and $<$ 1 year; subjects with overall survival \geq and $<$ 2 years; and subjects with overall survival \geq and $<$ 1.5 years. We will estimate Pearson correlation coefficients to assess the correlation of OS and PFS with electric field or specific absorption ratio parameters.

We may stratify the patients by MGMT methylation status, extent of resection, or a combination of the two.

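### The exploratory analyses relating modelled electric field to outcome are unadjusted for residual tumour volume, location and extent of resection, so an apparent field dose-response could arise without a device effect

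*Combined protocol and SAP*

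**What the plan says.** Section 2.1.2.6.2 sets the aim: "we will perform computer modeling of electric field and energy deposition in the tumor and then perform correlative analysis with respect to overall survival", PFS and response. Field modelling is listed among the tertiary/exploratory endpoints in Table 2. Section 6.3.2.2 fixes where the exposure is measured: "the electric field strength and the specific absorption ratio at the gross tumor volume will be tabulated". It then names the first test: "Spearman rank-order correlation will be performed between the non-parametric electrical and clinical outcome variables". Section 10.2.1 names two others. One is a set of two-group comparisons: "we will use the Wilcoxon rank sum test to compare the electric field and specific absorption ratio parameters between: responders and non-responders", and likewise for PFS split at 1 year and OS split at 2 and at 1.5 years. The other is a correlation: "We will estimate Pearson correlation coefficients to assess the correlation of OS and PFS with electric field or specific absorption ratio parameters". None of these has covariates.

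On what drives the field, Section 6.3.2 says that in grey and white matter it is strengthened or weakened "depending on the local tissue properties and the geometry of structures such as the frontal, temporal and posterior horns of the lateral ventricles". Section 2.1.2.6.2 likewise makes it depend on tissue properties and geometry.

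Three other sentences come near the question of confounding:
- Section 6.3.2.1: "secondary analyses will be performed to determine the extent of correlation with respect to patient age, Karnofsky Performance Status, dexamethasone dosage", then medications, treatment cycles, laboratory values and molecular markers. Tumour volume, location and resection are not listed, and the task is correlation, not adjustment.
- Section 10.2.1 allows a regression if confounders need handling, but as a rerun of the mutation-burden comparison between treatment groups.
- Section 10.2.1 closes by saying patients may be stratified by MGMT status, extent of resection or both. It does not say for which analysis.

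**The concern.** Field strength in the tumour is not assigned; it comes with the patient's anatomy. Eligibility leaves that anatomy free to vary: biopsy-only patients are admitted (Section 5.1), and only brain stem and cerebellar sites are excluded (Section 5.2). By naming extent of resection as a possible stratifier, the plan treats it as prognostically relevant. If a feature affects both the computed field and survival, an unadjusted test will pick up that feature and present it as a field effect.

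Section 2.1.2.6.2 describes the parameters as a way to compare dosage between patients, so a positive result invites reading as a dose-response for the device. This trial has no randomised comparison against which to check such a reading, and adjustment chosen after the results are seen would carry less weight than adjustment written down now.

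**Working it through.** **1. The plan's own figures.** The documents give no power, effect size or error rate for the field analysis, so there is nothing to reproduce for it directly. The survival inputs can be checked against Table 10 (90 treated, 90 historical controls, k = 2.0, 6-month gain):
- HR = (22/28)² = 0.617, so |ln HR| = 0.482.
- Expected deaths: 67.6 treated (follow-up uniform 24 to 60 months) and 74.5 controls (uniform 19.4 to 60 months, an assumption consistent with the stated chart-review window).
- Power = Φ(0.482/√(1/74.5 + 1/67.6) − 1.645) = Φ(1.23) = 0.890, against the stated 0.894.

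The survival model is therefore read correctly. Table 10 has no other bearing on this point.

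**2. Simulation with no field effect.** From Sections 10.1 and 10.2: N = 90, Weibull k = 2, median 22 months, follow-up uniform 24 to 60 months. Assumed, because the documents give no values: a prognostic anatomical feature Z (SD units) with hazard ratio h per SD, and correlation −r between field F and Z.
- F = −rZ + √(1−r²)·ε
- hazard scale λ = (ln 2/22²)·h^Z
- T = (−ln U/λ)^(1/2)

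F does not enter the hazard. Tests are two-sided at 5%. Pearson and Spearman use observed time, since the plan does not say how censoring is handled. The Wilcoxon split is at 24 months, where every simulated patient's status is known. There are 2,000 trials per cell (Monte Carlo SE at 5%: √(0.05×0.95/2000) = 0.5 points).

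Rejection rates (%), selected cells:

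| r | h | Wilcoxon | Spearman | Pearson | Cox, unadjusted | Cox, adjusted for Z | Cox, Z in two levels |
|---|---|---|---|---|---|---|---|
| 0 | 1.6 | 4.6 | 4.6 | 5.8 | 5.4 | 5.5 | 5.5 |
| 0.2 | 1.3 | 6.4 | 6.8 | 6.8 | 7.4 | 5.4 | 5.4 |
| 0.3 | 1.6 | 14.8 | 16.4 | 17.8 | 20.2 | 4.8 | 7.6 |
| 0.5 | 1.6 | 30.4 | 37.0 | 39.8 | 44.2 | 5.8 | 11.7 |
| 0.5 | 2.0 | 48.6 | 58.8 | 62.2 | 66.2 | 4.1 | 16.7 |

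Over all cells with r of 0.2 or more, the planned tests run from 6.4% to 62.2%. Adjustment for Z gives 4.1% to 6.0% over every cell, including r = 0. The unadjusted Cox column is for comparison only; the plan does not use that model.

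**3. Analytic check.** The spurious hazard ratio per SD of field should be near h^(−r). For r = 0.3, h = 1.6: exp(−0.3×0.470) = 0.87; simulated 0.88. For r = 0.5, h = 2.0: exp(−0.5×0.693) = 0.71; simulated 0.75, slightly nearer 1 because omitting Z from a Cox model attenuates it.

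**4. Other survival inputs.** With k = 1.8 and median 28 months, r of 0.3 or 0.5 and h of 1.3 or 1.6, the Wilcoxon test at 2 years rejects in about 7% to 28% of trials.

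**5. The plan's optional stratifier.** In the step 4 scenarios, a Wilcoxon test stratified on three resection levels gives about 5% to 6% if the levels are exact thirds of Z, and about 6% to 10% if they correlate about 0.8 with Z. With only two levels and a Cox model (step 2), 5.4% to 16.7% remains.

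**The case against.** The analysis is exploratory, with no alpha, power or decision attached. Extent of resection is not ignored: the plan names it as a stratifier, and step 5 shows that using it at three levels would remove most of the inflation if resection tracks the confounder well. Both points stand, and they limit the importance of the finding. They do not remove it, because the stratification is optional and not linked to the field tests, and location and residual volume would still be uncovered.

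Three stronger readings are tempting, and the documents support none of them:
- A reader might infer that small, well-resected tumours receive a higher computed field, so the bias must flatter the device. The documents say that anatomy and geometry affect the field; they do not say that residual size does, or in which direction. Confounding could equally hide a real association.
- A reader might infer that completely resected patients, presumably with better prognosis, drop out for lack of a gross tumour volume. Section 6.1.1.3.2 defines complete resection as enhancement under 10 mm, not absence of tumour, and Section 6.1.1.3 provides for FLAIR in non-enhancing disease. The plan leaves the definition of the volume open for these patients; it does not say they are excluded.
- A reader might treat the 62% as an estimate for this trial. It is the top of an assumed range.

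The number of field parameters tested is a separate multiplicity question and is not relied on here.

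**Conclusion.** The concern holds as a limitation of an exploratory analysis. As written, the plan relates the field at the tumour to OS, PFS and response without adjustment, while stating that anatomy shapes the field. A dose-response could therefore appear with no device effect, and the planned tests could not tell the two apart. The range in step 2 rests on assumed correlations and hazard ratios; near zero correlation the tests keep their nominal level, so the true bias may be small. That adjustment restores the nominal level assumes the confounder is measured and modelled adequately. The primary OS comparison is not affected.

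**What to change.** In Sections 10.2.1 and 6.3.2.2:
- Make the main field-outcome analysis a Cox model for OS, and one for PFS, on the baseline field parameter. Adjust for a short pre-specified list: log residual tumour volume, extent of resection, a coarse location term and KPS. Add age and MGMT status as a sensitivity analysis.
- Keep the Wilcoxon, Pearson and Spearman results as descriptive.
- Adjust the response analysis only as far as the number of responders allows; Table 4 rules out complete or partial response for patients with non-measurable disease only.
- Report how many patients have no definable gross tumour volume.
- Label the results hypothesis-generating.

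The list is short because deaths are limited. With three resection levels and a binary location term, the model has 1 (field) + 1 + 2 + 1 + 1 = 6 parameters, or 67.6/6 = 11 expected deaths each; adding age and MGMT makes 8, or about 8 each.

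The operative report is already required (Section 11.2.2). Tumour is not among the structures that Section 6.3.2.2 lists for segmentation, but parameters at the gross tumour volume cannot be computed without delineating it, so its volume should be obtainable. The cost is some SAP wording, slightly more analysis and wider intervals.
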